Laboratory data will be summarized by treatment arm and type of laboratory test. Reference ranges and markedly abnormal results (specified in the SAP) will be used in the summary of laboratory data. Descriptive statistics will be calculated for each laboratory analyte and for changes from Screening/Baseline at each scheduled time point. Laboratory abnormalities will be categorized according to analyte and graded according to DAIDS.

Descriptive statistics of vital signs including temperature, pulse/heart rate, body weight, and blood pressure (systolic and diastolic) [(supine)] values and changes from baseline will be summarized at each scheduled time point. The percentage of participants with values beyond clinically important limits will be summarized. Vital signs abnormalities will be categorized according to parameter and graded according to DAIDS.

Physical examination findings will be summarized at each scheduled time point. Descriptive statistics will be calculated at baseline and for observed values and changes from baseline at each scheduled time point. Frequency tabulations of the abnormalities will be made.

TMC114+JNJ-48763364-AAA+JNJ-35807551-AAA+JNJ-63625328-ZCA (darunavir 800 mg/cobicistat 150 mg/emtricitabine 200 mg/tenofovir alafenamide 10 mg)

[figure not shown]
Clinical Protocol TMC114FD2HTX4004 Amendment 3

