9.4.4. Safety Analyses

All safety analyses will be made on the Safety Population. For all safety endpoints descriptive statistics will be used to summarize the endpoints.

Adverse Events

The verbatim terms used in the CRF by investigators to identify AEs will be categorized according to system organ class and graded according to DAIDS as specified in Appendix 7: DAIDS Table for Grading the Severity of Adult and Pediatric Adverse Events. Any AE occurring at or after the initial administration of study intervention through the day of last dose plus 7 days is considered to be treatment-emergent. All reported treatment-emergent adverse events (TEAEs) will be included in the analysis. For each AE, the percentage of participants who experience at least 1 occurrence of the given event will be summarized by intervention arm.

Summaries, listings, datasets, or participant narratives may be provided, as appropriate, for those participants who die, who discontinue intervention due to an AE, or who experience a severe or a serious adverse event.

Clinical Laboratory Tests

Laboratory data will be summarized by treatment arm and type of laboratory test. Reference ranges and markedly abnormal results (specified in the Statistical Analysis Plan) will be used in the summary of laboratory data. Descriptive statistics will be calculated for all laboratory analyte for observed values and for changes from Screening/Baseline at each scheduled time point. Laboratory

abnormalities will be categorized according to analyte and graded according to DAIDS as specified in Appendix 7: DAIDS Table for Grading the Severity of Adult and Pediatric Adverse Events.

Vital Signs

Descriptive statistics of vital signs including temperature, pulse/heart rate, body weight, and blood pressure (systolic and diastolic) (supine) values and changes from baseline will be summarized at each scheduled time point. The percentage of participants with values beyond clinically important limits will be summarized. Vital signs abnormalities will be categorized according to parameter and graded according to DAIDS as specified in Appendix 7: DAIDS Table for Grading the Severity of Adult and Pediatric Adverse Events.

Physical Examination

Descriptive statistics of changes from baseline will be summarized at each scheduled time point.

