Blood Pressure Abnormalities¹ Hypertension (with the lowest reading taken after repeat testing during a visit) ≥ 18 years of age	140 to < 160 mmHg systolic OR 90 to < 100 mmHg diastolic	≥ 160 to < 180 mmHg systolic OR ≥ 100 to < 110 mmHg diastolic	≥ 180 mmHg systolic OR ≥ 110 mmHg diastolic	Life threatening consequences in a participant not previously diagnosed with hypertension (e.g., malignant hypertension) OR Hospitalization indicated	
< 18 years of age	> 120/80 mmHg	≥ 95 th to < 99 th percentile + 5 mmHg adjusted for age, height, and gender (systolic and/or diastolic)	≥ 99th percentile + 5 mmHg adjusted for age, height, and gender (systolic and/or diastolic)	Life threatening consequences in a participant not previously diagnosed with hypertension (e.g., malignant hypertension) OR Hospitalization indicated	
Hypotension	No symptoms	Symptoms corrected with oral fluid replacement	Symptoms AND IV fluids indicated	Shock requiring use of vasopressors or mechanical assistance to maintain blood pressure	
Cardiac Ischemia or Infarction Report only one	NA	NA	New symptoms with ischemia (stable angina) OR New testing consistent with ischemia	Unstable angina OR Acute myocardial infarction	
Heart Failure	No symptoms AND Laboratory or cardiac imaging abnormalities	Symptoms with mild to moderate activity or exertion	Symptoms at rest or with minimal activity or exertion (e.g., hypoxemia) OR Intervention indicated (e.g., oxygen)	Life threatening consequences OR Urgent intervention indicated (e.g., vasoactive medications, ventricular assist device, heart transplant)	

Blood pressure norms for children < 18 years of age can be found in: Expert Panel on Integrated Guidelines for Cardiovascular Health and Risk Reduction in Children and Adolescents. *Pediatrics* 2011;128;S213; originally published online November 14, 2011; DOI: 10.1542/peds.2009 2107C.

DAIDS AE Grading Table Corrected Version 2.1-July 2017 Page 31

Cardiovascular

PARAMETER	GRADE 1 MILD	GRADE 2 MODERATE	GRADE 3 SEVERE	GRADE 4 POTENTIALLY LIFE- THREATENING
Hemorrhage (with significant acute blood loss)	NA	Symptoms AND No transfusion indicated	Symptoms AND Transfusion of ≤ 2 units packed RBCs indicated	Life threatening hypotension OR Transfusion of > 2 units packed RBCs (for children, packed RBCs > 10 cc/kg) indicated

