7.3. Vital Signs and Physical Examination Findings

7.3.1. Definitions

The following vital signs parameters will be analyzed.

- Pulse (bpm)
- Systolic blood pressure, SBP (mmHg)
- Diastolic blood pressure, DBP (mmHg)

A listing of subjects with treatment-emergent clinically important vital signs will be presented, along with a listing of all vital sign measurements.

Table 5: Pulse, SBP and DBP are classified in the following abnormality codes.

	Pulse	DBP ^a	SBP ^a
Abnormality Code	(bpm)	(mmHg)	(mmHg)
Abnormally low	≤50	≤50	≤90
Grade 1 or mild	-	>90 - <100	>140 - <160
Grade 2 or moderate	-	≥100 - <110	≥ 160 - <180
Grade 3 or severe	-	≥110	≥180
Abnormally high	≥120	-	-

Classification of adverse events related to hypotension/hypertension should be done according to the DAIDS grading table (Appendix 7 at protocol).

In determining abnormalities, the following rules are applied:

- worst grades/abnormalities are determined over the whole observational period for each trial period separately, including post-reference scheduled *and* unscheduled measurements of that phase.
- The abnormalities 'abnormally low' and 'abnormally high'/grades are considered equally important, i.e. if a subject has as well an abnormally low as an abnormally high or graded value post-reference, both abnormalities are shown in the tables. (This means that the sum of the percentages can be more than 100%).

Definition treatment-emergent:

An abnormality will be considered treatment-emergent in a particular period if it is worse than the reference corresponding to this period. If the reference is missing, the abnormality is always considered as treatment-emergent. A shift from 'abnormally low' at reference to 'abnormally high' or 'grade' post reference (or vice versa) is also treatment-emergent.

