7.3.2. Analysis Methods

Continuous vital sign parameters including height, weight, pulse, blood pressure (systolic and diastolic), and Body Mass Index (BMI) will be summarized at each assessment time point by descriptive statistics (mean, standard deviation, median, minimum and maximum) per treatment arm.

Cross-tabulations for the worst abnormalities versus reference per vital signs test will be produced by treatment arm.

Descriptive statistics for the actual values and changes from baseline (including BMI, weight) per timepoint will be presented. The only reference time point that will be used to calculate these changes is the timepoint closest to the first drug intake after randomization.

BMI will be calculated as weight (kg)/(height (m²)), at each time point that body weight is measured. The height measurement collected at screening will be used in the calculation. The frequency tabulations will be presented for BMI as a categorical variable and the descriptive statistics will be summarized for BMI as a continuous variable.

Physical examination findings and changes from baseline at each scheduled time point will be tabulated per treatment arm. Abnormal physical examination findings will also be listed.

8. PATIENT REPORTED OUTCOMES (PROs)

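### SAP Table 5 starts Grade 1 blood pressure above 140/90, although the protocol promises DAIDS grading, which includes 140 and 90

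*Protocol*

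**What the plan says.** The protocol commits to DAIDS grading of vital signs twice. The synopsis says "Vital signs abnormalities will be categorized according to parameter and graded according to DAIDS". Section 9.4.4 repeats this and names the source: "Vital signs abnormalities will be categorized according to parameter and graded according to DAIDS as specified in Appendix 7". The DAIDS table in Appendix 7 gives Grade 1 hypertension for adults as "140 to < 160 mmHg systolic OR 90 to < 100 mmHg diastolic", with the qualifier "with the lowest reading taken after repeat testing during a visit".

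SAP Section 7.3.1, Table 5, sets the codes that will be programmed. Grade 1 (mild) is >140 to <160 systolic and >90 to <100 diastolic. Grade 2 is ≥160 to <180 and ≥100 to <110. Grade 3 is ≥180 and ≥110. The low codes are ≤90 systolic and ≤50 diastolic, and an abnormally high code exists only for pulse. A footnote to the table sends the classification of hypertension and hypotension adverse events to protocol Appendix 7.

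The SAP then uses these codes as follows:

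- Emergence (7.3.1): "An abnormality will be considered treatment-emergent in a particular period if it is worse than the reference corresponding to this period".
- Summary over time (7.3.1): "worst grades/abnormalities are determined over the whole observational period for each trial period separately", counting scheduled and unscheduled measurements.
- Output (7.3.2): "Cross-tabulations for the worst abnormalities versus reference per vital signs test will be produced by treatment arm".

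**The concern.** Table 5 uses DAIDS grade names, and its Grade 2 and Grade 3 bounds agree with Appendix 7. Only the lower bound of Grade 1 departs, and neither SAP Section 7.3 nor the SAP amendment history gives a reason. As printed, a systolic value of 140 or a diastolic value of 90 falls between the low code and Grade 1 and has no category.

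The gap matters because emergence is judged against a reference grade. Leaving out the boundary value changes the grade on both sides of that comparison, so cases can be missed as well as added. The outputs exposed are the worst-versus-reference cross-tabulations, the percentages with abnormal values and the listing of treatment-emergent vital signs. The same report could also disagree with itself: a reading of 140 could support a Grade 1 adverse event under the footnote and appear as no abnormality in the systolic table.

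**Working it through.** No planned figure depends on these cut-offs, so there is nothing in the plan to reproduce. The check has three steps.

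**Step 1: where the two rules differ.** Both rules were applied to every integer pair with systolic 91 to 220 and diastolic 51 to 130. For this step a participant takes the higher of the systolic and diastolic grades. They differ on 89 pairs:

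- systolic 140 with diastolic 51 to 90: 40 pairs
- diastolic 90 with systolic 91 to 140: 50 pairs
- less the pair 140/90, counted twice: 40 + 50 − 1 = 89

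In all 89, DAIDS gives Grade 1 and Table 5 gives nothing. Taking both parameters together, 140 is rescued when diastolic exceeds 90, and 90 is rescued when systolic exceeds 140. The cross-tabulations are made per vital signs test, however, so in the systolic table 140 is ungraded whatever the diastolic value.

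**Step 2: effect on emergence** (emergent if the later grade is worse than the reference grade).

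| Reference → later | DAIDS grades | DAIDS emergent | Table 5 grades | Table 5 emergent |
|---|---|---|---|---|
| 140/80 → 141/80 | 1 → 1 | no | none → 1 | yes |
| 130/90 → 130/91 | 1 → 1 | no | none → 1 | yes |
| 139/80 → 140/80 | none → 1 | yes | none → none | no |
| 130/89 → 130/90 | none → 1 | yes | none → none | no |
| 139/80 → 141/80 | none → 1 | yes | none → 1 | yes |

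The first two rows are false emergent codes and the next two are missed ones.

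**Step 3: illustrative size.** These inputs are assumptions, because the documents give no blood pressure distribution: integer readings, normal distributions, systolic mean 125 to 132 (SD 14 to 16), diastolic mean 78 to 82 (SD 9 to 10), within-person correlation 0.6, and systolic–diastolic correlation 0.6.

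The share of DAIDS Grade 1 readings that sit on the boundary is P(140) / P(140 to 159) for systolic and P(90) / P(90 to 99) for diastolic:

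- systolic, mean 125, SD 14: 1.61% / 14.33% = 11%
- systolic, mean 132, SD 16: 2.20% / 27.68% = 8%
- diastolic, mean 78, SD 9: 1.82% / 9.22% = 20%
- diastolic, mean 82, SD 10: 2.90% / 18.66% = 16%

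Simulating Weeks 4, 12 and 24 at three settings across this range, the participants with any hypertension grade were, DAIDS against Table 5:

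- 36.9% against 33.1%: difference 3.8 points, and 0.038 × 55 = 2.1 per arm
- 50.8% against 47.1%: difference 3.7 points, and 0.037 × 55 = 2.0 per arm
- 62.8% against 59.3%: difference 3.5 points, and 0.035 × 55 = 1.9 per arm

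Adding a baseline visit and applying the SAP emergence rule gives about 1.1 to 1.8 missed emergent cases and about 0.4 to 0.7 false ones per 55-participant arm, for each parameter. Missed cases are the larger error.

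**After the change.** With the Grade 1 lower bounds at ≥140 and ≥90, the two rules agree on every integer pair tested. The change from 140/80 to 141/80 is no longer emergent, and 139/80 to 140/80 is.

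**The case against.** The strongest case against is that this is one boundary value per parameter, in the lowest grade, in descriptive tables. Hypertension adverse events are still classified by DAIDS under the footnote. The blood pressure secondary endpoint is the continuous change in systolic and diastolic pressure from baseline, which Table 5 does not touch. All vital-sign measurements are also listed, so the boundary readings stay visible. The same coding applies to both arms. The size estimate rests wholly on assumed distributions. All of this stands, and it limits the importance of the point. It does not remove the contradiction between the protocol's stated grading and the SAP's cut-offs. A text-extraction fault is an unlikely explanation, because the ≥ signs survive in the Grade 2 and Grade 3 rows of the same table.

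Two stronger readings are tempting, and the documents do not support them.

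- A reader might infer that the SAP reports a 1 mmHg rise as new hypertension. What it produces is a treatment-emergent Grade 1 vital-sign code, not an adverse event. A worst later reading exactly 1 mmHg above a boundary baseline is rare under the same assumptions, at about 0.06% to 0.17% of participants.
- A reader might infer that taking the worst value contradicts the DAIDS instruction to grade the lowest repeat reading. The DAIDS instruction concerns repeats within one visit, and the SAP rule summarises over a whole period. The two can be applied together. The protocol's blood pressure procedures schedule no repeat reading within a visit, so the SAP is at most silent on that case.

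**Conclusion.** The point holds as a boundary inconsistency. Protocol synopsis and Section 9.4.4 promise DAIDS grades, and SAP Table 5 does not deliver them at exactly 140 systolic or exactly 90 diastolic. The worst-versus-reference tables, abnormality percentages and treatment-emergent listing would therefore differ from the DAIDS results they are labelled as, with errors in both directions.

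The contradiction itself needs no assumption. Its size does: about 2 of 55 participants per arm losing a Grade 1 code is illustrative, and depends on the assumed means, SDs, correlations and integer recording. Digit preference in manual readings, which the protocol allows when no automated device is available, could make 140 and 90 more common than a normal model implies.

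The primary endpoint, mean blood pressure changes and reported adverse events are unaffected. No direction of bias between arms is shown. It is a small error, worth correcting because the correction is specific and nearly free.

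**What to change.** In SAP Table 5, set Grade 1 to ≥140 to <160 mmHg systolic and ≥90 to <100 mmHg diastolic, matching protocol Appendix 7. Leave Grades 2 and 3 as they are, since they already agree. If the sponsor intended a different Grade 1 bound, the SAP should say so, give the reason and drop the DAIDS grade labels.

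Optionally, add a sentence saying which reading is graded if blood pressure is repeated within a visit, before the worst grade over the period is taken. This is clarification, not correction.

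The cost is one SAP wording change and a small edit to the grade derivation, with the affected tables and listing re-run if already produced. No new data are needed.

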1.2. Schema

Figure 1: Schematic Overview of the Study

Abbreviations: ARV = antiretroviral; C = cobicistat; D = darunavir; F or FTC = Emtricitabine; INI = integrase inhibitor; QD = once a day; TAF = Tenofovir Alafenamide

1.3. Schedule of Activities (SoA)

Phase	Screeninga	Baseline		48-Weeks Treatment Phase ^c					ESIDe	30-Day FU ^f	Remarks
Visit		Day 1 ^b	Week 4	Week 12	Week 24	Week 28 ^d	Week 36	Week 48			
Study Procedures										_	
Screening/Administrative											
Informed consent	X										Must be obtained before the first study related activity.
Medical history	X										
Height	Х										Measured using a wall mounted stadiometer or one mounted on a balance beam scale, whichever is most appropriate for the individual participant. Participants should be wearing socks or barefoot and should not be wearing shoes.
HBV and HCV testing	X										
Serum pregnancy test	X										Females of childbearing potential only; at central laboratory
FSH test	X										FSH test for female participants who have stopped menstruating for at least 2 years but do not have documentation of ovarian failure.
Inclusion/exclusion criteria	X	Х									If a participant's clinical status changes (including any available laboratory results or receipt of additional medical records) after screening but before the first dose of D/C/F/TAF FDC is given such that he/she no longer meets all eligibility criteria, then the participant should be excluded.
Study Intervention											
Randomization		X									Randomization should be performed on the same day as the baseline visit, provided that all screening procedures have been completed and participant eligibility has been confirmed.
D/C/F/TAF Dispensation/Accountability		X	X	X	X		X	X	X		Immediate Switch Arm
D/C/F/TAF Dispensation/Accountability					X	X	X	X	X		Delayed Switch Arm

Phase	Screening ^a	Baseline		48-W	eeks Trea	atment P	hase ^c		ESIDe	30-Day FU ^f	Remarks
Visit		Day 1 ^b	Week 4	Week 12	Week 24	Week 28 ^d	Week 36	Week 48			
Study Procedures											
Adherence		Х	X	X	X	X	X	X	X		Treatment adherence will be assessed by participant self report using a 4 day recall during study visit.
Safety Evaluations											
Vital signs	X	X	X	X	X	X	X	X	X	X	BP, pulse rate (supine after at least 5 minutes rest)
Body weight	X	X	Х	Х	Х	Х	Х	Х	X	X	Attention should be given to weigh the participant on the same scale through the duration of the study. Participants should be weighed wearing underwear and a gown; participants will be instructed to take off their shoes and to empty their bladders before being weighed. Note: if disrobing for weighing is logistically impossible, the participant must be dressed as lightly as possible, with consistency from visit to visit
Waist Circumference Measurement	X	X	Х	X	X	X	Х	Х	Х		Measured with the participant standing, wearing underwear, with or without a gown. The measurement will be performed at a level midway between the superior aspect of the iliac crests and the lower lateral margin of the ribs. The measurement need not be at the level of the umbilicus. The measuring tape will be kept horizontal.
Body Composition via DEXA scan		X			X			Х	Х		Performed between screening and baseline (+2 weeks), at Weeks 24, 48, and the ESID visit (±10 days) (only to be performed at ESID if the last scan is more than 12 weeks from the date of the ESID visit and the ESID visit takes place before Week 48). A rescan for technical reasons at all scheduled time points is allowed within 2 weeks.
Complete physical examination	X	X						X	X		
Symptom-directed physical examination			X	X	X	X	X			X	May be conducted at all other scheduled/unscheduled study visits based on reported safety or tolerability issues.
Concomitant medications	X	X	X	X	X	X	X	X	X	X	

Phase	Screeninga	Baseline		48-W	eeks Tre	atment P	hase ^c	ESIDe	30-Day FU ^f	Remarks	
Visit		Day 1 ^b	Week 4	Week 12	Week 24	Week 28 ^d	Week 36	Week 48			
Study Procedures											
Adverse events (AEs)	X	X	X	X	X	X	X	X	X	X	In the setting of a suspected renal AE, serum creatinine and urine chemistry will be assessed (creatinine, sodium, phosphate, glucose, protein, albumin).
Fasting Clinical Laboratory Tests											
Chemistry profile	X	X	X	X	X	X	X	X	X	X	
Metabolic profile		X			X			X	X		If a participant has not fasted prior to the visit, the visit may proceed, but participant must return within 72 hours in a fasted state to have a blood draw.
Leptin and Adiponectin		X			X			X	X		
Alpha Melanocyte-Stimulating Hormone		X			X			X	X		
Hematology profile	X	X	X	X	X	X	X	X	X	X	
eGFRcr	X	X	X	X	X	X	X	X	X	X	eGFRcr by Cockcroft Gault
Urinalysis	X	X	X	X	X	X	X	X	X	X	Dipstick. If dipstick results are abnormal, the sediment will be examined microscopically.
Urine Pregnancy test		X	Х	X	X	X	X	X	X	X	Females of childbearing potential only. Additional serum or urine pregnancy tests may be performed, as determined necessary by the investigator, to establish the absence of pregnancy throughout the study.
Efficacy Evaluations											
Plasma HIV-1 RNA	Х	X	X	X	X	X	X	Х	X	X	If the HIV 1 RNA value is ≥50 copies/mL a retest should be collected at a scheduled or unscheduled visit, 2 to 4 weeks after availability of the results (except for screening and baseline results). Leftover blood samples from the HIV 1 RNA determinations could be used for protocol related testing (virology, safety, PK analysis) at additional time points.
CD4 ⁺ cell count	X	X			X			X	X	X	

Phase	Screening ^a	Baseline	48-Weeks Treatment Phase ^c						ESID ^e	30-Day FU ^f	Remarks
Visit		Day 1 ^b	Week 4	Week 12	Week 24	Week 28 ^d	Week 36	Week 48			
Study Procedures											
HIV-1 genotype/phenotype			X	X	X	X	X	X	X		Performed using PhenoSense GT® Plus Integrase for participants with confirmed virologic rebound (2 consecutive HIV 1 RNA values ≥200 copies/mL at a scheduled or unscheduled visit after maintaining HIV 1 RNA <50 copies/mL) and a HIV 1 RNA >400 copies/mL at the time of confirmed rebound or later timepoints; confirmatory testing should be conducted 2 to 4 weeks after the initial HIV 1 RNA ≥200 copies/mL.
Whole blood sample storage		X									Will be stored and analyzed using Genosure Archive® if deemed necessary by the sponsor to characterize archived viral resistance.
Patient Reported Outcomes											
Dispense PRO device	Х										Device for PROs will be dispensed to all participants during the Screening visit so the participant can complete the 7 days (prebaseline) DAILY EATS. The participants should bring PRO device to required study visits.
DAILY EATS		X			Х			Х			Completed at home for 7 consecutive days prior to the visit. Study staff should contact the participants prior to the visits to remind the participant to complete the 7 day DAILY EATS.
BSQ-8D		X			X			X	X		
HIV-SI		X			X			X	X		Should be completed during the study visit before all other study related procedures to prevent influencing participant perceptions; PGIC and PGIC S should be completed after the BSQ 8D and HIV SI.
PGIC					X			X	X		

Phase	Screeninga	48-Weeks Treatment Phase ^c						ESIDe	30-Day FU ^f	Remarks	
Visit		Day 1 ^b	Week 4	Week 12	Week 24	Week 28 ^d	Week 36	Week 48			
Study Procedures											
Other											
Plasma sample storage		X	X	X	X	X	X	X	X		Banked for possible additional protocol related testing (virology, safety). Plasma concentrations of DRV and COBI may be determined in participants experiencing virologic rebound or participants who discontinue the study early and have HIV 1 RNA ≥50 copies/mL using stored blood samples collected throughout the study, if deemed necessary. Plasma concentrations of INIs for the Delayed Switch arm may be determined in participants experiencing virologic rebound using stored blood samples collected throughout the study, if deemed necessary.

AE: adverse events; BP: blood pressure; BSQ 8D: Body Shape Questionnaire; C: cobicistat (Cobi); cm: centimeters; D: darunavir (DRV); DEXA: dual energy X ray absorptiometry; ESID: Early Study Intervention Discontinuation visit; eGFRcr: Creatinine based estimated glomerular filtration rate; F: Emtricitabine; FDC: fixed dose combination; FSH: follicle stimulating hormone; FU: Follow up; HBV: hepatitis B; HCV: hepatitis C; HIV 1 RNA: human immunodeficiency virus type 1 ribonucleic acid; HIV SI: HIV Symptom Index; PGIC: Patient Global Impression of Change; PGIC S: Patient Global Impression of Change—satiety; PRO: patient reported outcome; TAF: tenofovir alafenamide.

Unscheduled visit(s) may be required for safety reasons, for technical issues with the samples, or for confirmation of virologic rebound. When human immunodeficiency virus (HIV) 1 ribonucleic acid (RNA) repeat testing is required at an unscheduled visit, an HIV 1 genotype/phenotype plasma sample and a plasma storage sample should also be drawn at the same unscheduled visit.

- Evaluations to be completed within 30 days prior to baseline (Day 1). The Screening Phase may be extended on a case by case basis after discussion with the sponsor; however, no extensions beyond 6 weeks will be allowed.
- b The baseline visit (Day 1) cannot proceed until the investigator has received all results of the screening visit and participant eligibility has been confirmed. Participants randomized to the D/C/F/TAF fixed dose combination (FDC) treatment arm (Immediate Switch) will be dispensed D/C/F/TAF FDC at the baseline visit; initiation of treatment with D/C/F/TAF FDC must take place within 24 hours after the baseline visit
- c All study visits are to be scheduled relative to the baseline visit date (Day 1) and are to occur at the end of Weeks 4, 12, 24, 36 and 48. The visit window is ±7 days of the protocol specified date through Week 48.
- d For participants randomized to the Delayed Switch arm; 4 weeks after switch to D/C/F/TAF FDC.
- e Participants who prematurely discontinue or change study intervention during the treatment phase (from Day 1 to Week 48) will be required to complete the early study intervention discontinuation (ESID) visit assessments within 1 week of stopping/changing study intervention.
- f Required for any participant who has an ongoing adverse event (AE) or serious adverse event (SAE) at the time of his/her last study visit (unless consent is withdrawn); ±7 days window may be used.

